## APPENDIX 2 ADVERSE EVENT REPORTING

- All Serious Adverse Events (SAEs) that occur following the subject's written consent to participate in the study through 100 days of discontinuation of dosing must be reported to BMS Worldwide Safety.
- If the BMS safety address is not included in the protocol document (e.g. multicenter studies where events are reported centrally), the procedure for safety reporting must be reviewed/approved by the BMS Protocol Manager. Procedures for such reporting must be reviewed and approved by BMS prior to study activation.
- The BMS SAE form should be used to report SAEs. If the BMS form cannot be used, another acceptable form (i.e. CIOMS or Medwatch) must be reviewed and approved by BMS. The BMS protocol ID number must be included on whatever form is submitted by the Sponsor/Investigator.
- Following the subject's written consent to participate in the study, all SAEs, whether related or not related to study drug, are collected, including those thought to be associated with protocol-specified procedures. The investigator should report any SAE occurring after these time periods that is believed to be related to study drug or protocol-specified procedure.
- In accordance with local regulations, BMS will notify investigators of all reported SAEs that are suspected (related to the investigational product) and unexpected (i.e., not previously described in the IB). In the European Union (EU), an event meeting these criteria is termed a Suspected, Unexpected Serious Adverse Reaction (SUSAR). Investigator notification of these events will be in the form of an expedited safety report (ESR).
  - Other important findings which may be reported by the as an ESR include: increased frequency of a clinically significant expected SAE, an SAE considered associated with study procedures that could modify the conduct of the study, lack of efficacy that poses significant hazard to study subjects, clinically significant safety finding from a nonclinical (eg, animal) study, important safety recommendations from a study data monitoring committee, or sponsor decision to end or temporarily halt a clinical study for safety reasons.
  - Upon receiving an ESR from BMS, the investigator must review and retain the ESR with the IB. Where required by local regulations or when there is a central IRB/IEC for the study, the sponsor will submit the ESR to the appropriate IRB/IEC. The investigator and IRB/IEC will determine if the informed consent requires revision. The investigator should also comply with the IRB/IEC procedures for reporting any other safety information.
  - In addition, suspected serious adverse reactions (whether expected or unexpected) shall be reported by BMS to the relevant competent health authorities in all concerned countries according to local regulations (either as expedited and/or in aggregate reports).
- An SAE report should be completed for any event where doubt exists regarding its seriousness.
- For studies with long-term follow-up periods in which safety data are being reported, include the timing of SAE collection in the protocol.

- If the investigator believes that an SAE is not related to study drug, but is potentially related to the conditions of the study (such as withdrawal of previous therapy or a complication of a study procedure), the relationship should be specified in the narrative section of the SAE Report Form.
- If only limited information is initially available, follow-up reports are required. (Note: Follow-up SAE reports should include the same investigator term(s) initially reported.)
- If an ongoing SAE changes in its intensity or relationship to study drug or if new information becomes available, a follow-up SAE report should be sent within 24 hours to BMS using the same procedure used for transmitting the initial SAE report. All SAEs should be followed to resolution or stabilization. All SAEs should be followed to resolution or stabilization.

## **ADVERSE EVENTS**

An Adverse Event (AE) is defined as any new untoward medical occurrence or worsening of a preexisting medical condition in a clinical investigation subject administered an investigational (medicinal) product and that does not necessarily have a causal relationship with this treatment. An AE can therefore be any unfavorable and unintended sign (such as an abnormal laboratory finding), symptom, or disease temporally associated with the use of investigational product, whether or not considered related to the investigational product.

The causal relationship to study drug is determined by a physician and should be used to assess all adverse events (AE). The causal relationship can be one of the following:

Related: There is a reasonable causal relationship between study drug administration and the AE.

Not related: There is not a reasonable causal relationship between study drug administration and the AE.

The term "reasonable causal relationship" means there is evidence to suggest a causal relationship.

Adverse events can be spontaneously reported or elicited during open-ended questioning, examination, or evaluation of a subject. (In order to prevent reporting bias, subjects should not be questioned regarding the specific occurrence of one or more AEs.)

## **NONSERIOUS ADVERSE EVENT**

A *nonserious adverse event* is an AE not classified as serious.

### **Nonserious Adverse Event Collection and Reporting**

The collection of nonserious AE information should begin at initiation of study drug. All nonserious adverse events (not only those deemed to be treatment-related) should be collected continuously during the treatment period and for a minimum of 100 days following the last dose of study treatment.

Nonserious AEs should be followed to resolution or stabilization, or reported as SAEs if they become serious. Follow-up is also required for nonserious AEs that cause interruption or discontinuation of study drug and for those present at the end of study treatment as appropriate.

### **Laboratory Test Abnormalities**

All laboratory test results captured as part of the study should be recorded following institutional procedures. Test results that constitute SAEs should be documented and reported as such.

The following laboratory abnormalities should be documented and reported appropriately:

- any laboratory test result that is clinically significant or meets the definition of an SAE

- any laboratory abnormality that required the subject to have study drug discontinued or interrupted
- any laboratory abnormality that required the subject to receive specific corrective therapy.

### **Pregnancy**

If, following initiation of the investigational product, it is subsequently discovered that a study subject is pregnant or may have been pregnant at the time of investigational product exposure, including during at least 6 half lives after product administration, the investigational product will be permanently discontinued in an appropriate manner (eg, dose tapering if necessary for subject safety).

The investigator must immediately notify Worldwide Safety @BMS of this event via the Pregnancy Surveillance Form in accordance with SAE reporting procedures.

Follow-up information regarding the course of the pregnancy, including perinatal and neonatal outcome and, where applicable, offspring information must be reported on the Pregnancy Surveillance Form [provided upon request from BMS]

Any pregnancy that occurs in a female partner of a male study participant should be reported to BMS. Information on this pregnancy will be collected on the Pregnancy Surveillance Form.

### **Overdose**

An overdose is defined as the accidental or intentional administration of any dose of a product that is considered both excessive and medically important. All occurrences of overdose must be reported as an SAE.

### **Other Safety Considerations**

Any significant worsening noted during interim or final physical examinations, electrocardiograms, x-rays, and any other potential safety assessments, whether or not these procedures are required by the protocol, should also be recorded as a nonserious or serious AE, as appropriate, and reported accordingly.

[figure not shown]
## APPENDIX 3: MANAGEMENT ALGORITHMS

- These general guidelines constitute guidance (adherence is not required) to the Investigator. The guidance applies to all immuno-oncology (I-O) agents and regimens.
- A general principle is that differential diagnoses should be diligently evaluated according to standard medical practice. Non-inflammatory etiologies should be considered and appropriately treated.
- Corticosteroids are a primary therapy for immuno-oncology drug-related adverse events. The oral equivalent of the recommended IV doses may be considered for ambulatory patients with low-grade toxicity. The lower bioavailability of oral corticosteroids should be taken into account when switching to the equivalent dose of oral corticosteroids.
- Consultation with a medical or surgical specialist, especially prior to an invasive diagnostic or therapeutic procedure, is recommended.
- The frequency and severity of the related adverse events covered by these algorithms will depend on the immuno-oncology agent or regimen being used

Investigators should refer to the most current version of the nivolumab or ipilimumab IB for current recommendations for management of a specific Adverse Event of interest.

[figure not shown]
Information must be included in the protocol. The format should be that which is acceptable per institutional practices or procedures:

1. As an appendix to a protocol document [may necessitate a change/amendment to the protocol as information is updated]
2. As reference to the current version of the reference IB in the protocol or
3. As text in the protocol.

## GI Adverse Event Management Algorithm

Rule out non-inflammatory causes. If non-inflammatory cause is identified, treat accordingly and continue I-O therapy. Opiates/narcotics may mask symptoms of perforation. Infliximab should not be used in cases of perforation or sepsis.

[figure not shown]

Patients on IV steroids may be switched to an equivalent dose of oral corticosteroids (e.g. prednisone) at start of tapering or earlier, once sustained clinical improvement is observed. Lower bioavailability of oral corticosteroids should be taken into account when switching to the equivalent dose of oral corticosteroids.

Updated 05-Jul-2016

## Renal Adverse Event Management Algorithm

Rule out non-inflammatory causes. If non-inflammatory cause, treat accordingly and continue I-O therapy

[figure not shown]

Patients on IV steroids may be switched to an equivalent dose of oral corticosteroids (e.g. prednisone) at start of tapering or earlier, once sustained clinical improvement is observed. Lower bioavailability of oral corticosteroids should be taken into account when switching to the equivalent dose of oral corticosteroids.

Updated 05-Jul-2016

## Pulmonary Adverse Event Management Algorithm

Rule out non-inflammatory causes. If non-inflammatory cause, treat accordingly and continue I-O therapy. Evaluate with imaging and pulmonary consultation.

[figure not shown]

Patients on IV steroids may be switched to an equivalent dose of oral corticosteroids (e.g. prednisone) at start of tapering or earlier, once sustained clinical improvement is observed. Lower bioavailability of oral corticosteroids should be taken into account when switching to the equivalent dose of oral corticosteroids.

Updated 05-Jul-2016

## Hepatic Adverse Event Management Algorithm

Rule out non-inflammatory causes. If non-inflammatory cause, treat accordingly and continue I-O therapy. Consider imaging for obstruction.

Patients on IV steroids may be switched to an equivalent dose of oral corticosteroids (e.g. prednisone) at start of tapering or earlier, once sustained clinical improvement is observed. Lower bioavailability of oral corticosteroids should be taken into account when switching to the equivalent dose of oral corticosteroids.

[figure not shown]
\*I-O therapy may be delayed rather than discontinued if AST/ALT  $\leq$  8 x ULN or T.bili  $\leq$  5 x ULN.

\*\*The recommended starting dose for grade 4 hepatitis is 2 mg/kg/day methylprednisolone IV.

Updated 05-Jul-2016

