### **Dose Delay Criteria**

**Because of the potential for clinically meaningful nivolumab-related AEs requiring early recognition and prompt intervention, management algorithms have been developed for suspected AEs of selected categories.**

Dose delay criteria, treatment resumption criteria, drug discontinuation criteria, and management algorithms described in this section and Appendix 3 are applicable for drug-related adverse events (adverse events that are possibly, probably, or definitely related to nivolumab, ipilimumab, or both). All study drugs must be delayed until treatment can resume.

Nivolumab and ipilimumab administration should be delayed for the following:

- Any Grade  $\geq$  2 non-skin, drug-related adverse event with the exception of fatigue, medically managed hypothyroidism or hyperthyroidism, tolerable Grade 2 AEs (except for grade 2 uveitis discussed below), and Grade 2 laboratory abnormalities other than Grade 2 creatinine, AST, ALT, and/or total bilirubin abnormalities
- Grade 2 drug-related creatinine, AST, ALT, and/or total bilirubin abnormalities.
- Any Grade 3 skin, drug-related adverse event
- Any Grade 3 drug-related laboratory abnormality, with the following exceptions:
  - Grade 3 or 4 lymphopenia or asymptomatic amylase or lipase abnormalities do not require a dose delay

- Grade  $\geq$  3 AST, ALT, total bilirubin will require dose discontinuation
- Any adverse event, laboratory abnormality, or intercurrent illness which, in the judgment of the investigator, warrants delaying the dose of study medication.

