### **Discontinuation Criteria**

Treatment should be permanently discontinued for the following:

- Any Grade 2 drug-related uveitis, eye pain or blurred vision that does not respond to topical therapy and does not improve to Grade 1 severity within the re-treatment period OR requires systemic treatment
- Any Grade 3 non-skin, drug-related adverse event lasting  $>$  7 days with the following exceptions for laboratory abnormalities, diarrhea, colitis, neurologic toxicity, drug-related

uveitis, pneumonitis, bronchospasm, hypersensitivity reactions, infusion reactions, and endocrinopathies:

- Grade 3 drug-related diarrhea, colitis, neurologic toxicity, uveitis, pneumonitis, bronchospasm, hypersensitivity reaction, or infusion reaction of any duration requires discontinuation
- Grade 3 drug-related endocrinopathies, adequately controlled with only physiologic hormone replacement do not require discontinuation. Adrenal insufficiency requires discontinuation regardless of control with hormone replacement.
- Grade 3 drug-related laboratory abnormalities do not require treatment discontinuation except:
  - Grade 3 drug-related thrombocytopenia > 7 days or associated with bleeding requires discontinuation
  - Any drug-related liver function test (LFT) abnormality that meets the following criteria require discontinuation:
    - o Grade  $\geq$  3 drug-related AST, ALT or Total Bilirubin requires discontinuation\*
    - o Concurrent AST or ALT > 3 x ULN and total bilirubin > 2x ULN

\*In most cases of Grade 3 AST or ALT elevation, study drug(s) will be permanently discontinued. If the investigator determines a possible favorable benefit/risk ratio that warrants continuation of study drug(s), a discussion between the investigator and the BMS Medical Monitor/designee must occur.

- Any Grade 4 drug-related adverse event or laboratory abnormality (including but not limited to creatinine, AST, ALT, or Total Bilirubin), except for the following events which do not require discontinuation:
  - Grade 4 neutropenia  $\leq$  7 days
  - Grade 4 lymphopenia or leukopenia or asymptomatic amylase or lipase
  - Isolated Grade 4 electrolyte imbalances/abnormalities that are not associated with clinical sequelae and are corrected with supplementation/appropriate management within 72 hours of their onset

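### Section 11.0 and Appendix 3 give inconsistent dispositions for Grade 3 or higher and combined liver-test rises, and no sentence says which text prevails

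*Combined protocol and SAP*

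**What the plan says.** Four places in the protocol deal with drug-related liver-test rises.

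- **Section 11.0, Dose Delay Criteria.** For Grade 3 or higher: "AST, ALT, total bilirubin will require dose discontinuation". No exception is attached. The same subsection says that the "management algorithms described in this section and Appendix 3 are applicable for drug-related adverse events".
- **Section 11.0, Criteria to Resume Treatment.** Isolated Grade 2 rises may resume on return to baseline, once any steroid management is complete. Combined Grade 2 AST/ALT and bilirubin values that meet the discontinuation parameters are to be permanently discontinued.
- **Section 11.0, Discontinuation Criteria.** Grade 3 or higher "drug-related AST, ALT or Total Bilirubin requires discontinuation", marked with an asterisk. The footnote reads "In most cases of Grade 3 AST or ALT elevation, study drug(s) will be permanently discontinued". If the investigator sees a possibly favourable benefit/risk balance for continuing, "a discussion between the investigator and the BMS Medical Monitor/designee must occur". A separate line, with no asterisk, requires discontinuation for "Concurrent AST or ALT > 3 x ULN and total bilirubin > 2x ULN". A further line requires it for "Any Grade 4 drug-related adverse event or laboratory abnormality (including but not limited to creatinine, AST, ALT, or Total Bilirubin"), and none of the exceptions listed there is a liver test.
- **Appendix 3, Hepatic Adverse Event Management Algorithm.** A footnote says "I-O therapy may be delayed rather than discontinued if AST/ALT" is at or below 8 x ULN or total bilirubin is at or below 5 x ULN.

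Both Section 11.0 (Management Algorithms for Immuno-Oncology Agents) and the opening of Appendix 3 describe the algorithms as guidance that need not be followed.

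**The concern.** The rules can give different answers for the same blood result. Within Section 11.0, one subsection states an unqualified requirement and another qualifies it. The qualification is itself unclear in scope, because its marker sits on a line covering all three tests at Grade 3 or higher while its text names two tests at Grade 3. Appendix 3 then allows a delay over a range of values for which Section 11.0 requires discontinuation.

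What is at stake is mainly patient safety: whether treatment ends or is held after liver injury could depend on which page a site consults. There is also a consistency cost, since discontinuations for hepatic toxicity would not mean the same thing from one patient to the next. That second point is secondary. Section 14.0 assesses safety through adverse events, laboratory data and vital signs, and does not list a discontinuation rate as a measure.

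**Working it through.** The plan has no figure to reproduce here. The check compares the rules and applies their own thresholds.

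**Step 1: Dose Delay Criteria against Discontinuation Criteria.** Take a Grade 3 ALT rise with normal bilirubin. Dose Delay Criteria requires discontinuation and offers nothing else. Discontinuation Criteria requires it unless the footnote route is used. The line and its footnote are rule and exception, so they do not contradict each other; the mismatch is with Dose Delay Criteria, which lacks the exception. For Grade 3 bilirubin, the asterisk suggests that the exception applies and the footnote text does not mention it. For Grade 4, the asterisked line again includes it, the footnote does not, and the separate Grade 4 line requires discontinuation.

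**Step 2: the combined criterion against Appendix 3.** Both are stated in multiples of ULN, so no grading table is needed.

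- Combined criterion: AST or ALT > 3 and bilirubin > 2, so discontinue.
- Appendix 3 limits: AST/ALT ≤ 8, bilirubin ≤ 5, so delay is allowed.
- Example: AST 6, bilirubin 2.5. Since 6 > 3 and 2.5 > 2, the combined criterion is met. Since 6 ≤ 8 and 2.5 ≤ 5, both Appendix 3 limits are met.

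Even on the narrower reading, in which both Appendix 3 limits must hold, the overlap is AST or ALT above 3 and up to 8 x ULN together with bilirubin above 2 and up to 5 x ULN. The conflict therefore does not depend on how *or* is read.

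**Step 3: isolated Grade 3 rises against Appendix 3.** The documents grade by CTCAE 4.0 but give no ULN cut-points for liver tests. Assume that Grade 3 begins at L x ULN for AST/ALT and M x ULN for bilirubin. The overlap then runs from L to 8 for any L below 8, and from M to 5 for any M below 5; it is empty only if L is 8 or more and M is 5 or more. The footnote's contrast between delaying and discontinuing implies that it is not empty.

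**Step 4: what follows a delay.** Section 11.0 treats a delay as lasting until treatment can resume. The liver-specific resumption lines cover Grade 2 and combined Grade 2 rises. An isolated Grade 3 rise held under Appendix 3 would fall to the general rule, which is resolution to Grade 1 or lower or to baseline.

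**Step 5: how many patients.** Section 3.0 (Melanoma) gives drug-related Grade 3-4 rates from 407 pooled patients on a different combination schedule: ALT 8.4%, AST 5.9%. The maximum enrolment is 64 (Section 14.0).

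- ALT: 64 x 0.084 = 5.4
- AST: 64 x 0.059 = 3.8

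If those rates carried over, these would be ceilings. They include Grade 4 events and any values above 8 x ULN. The two groups overlap to an unknown extent, so the figures should not be added. Section 3.0 gives no pooled Grade 3-4 rate for bilirubin and none for the combined pattern.

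**The case against.** The best reply is that Appendix 3 is expressly non-binding, so its permissive footnote cannot compete with a requirement in Section 11.0. The sentence calling the algorithms applicable can also be read as setting scope (drug-related events) and not rank. This has force and makes the conflict milder than one between two mandatory rules. It does not remove it. Saying that guidance need not be followed is different from saying that Section 11.0 overrides a permission the guidance gives, and no sentence says the latter. The mismatch in Step 1 lies wholly inside Section 11.0 and is untouched by the status of Appendix 3.

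A reader might infer more than the documents support:

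- *That Appendix 3 authorises re-dosing.* It permits a delay. Resumption is governed by Criteria to Resume Treatment, which repeats permanent discontinuation for combined Grade 2 rises that meet the parameters.
- *That AST far above 8 x ULN with normal bilirubin qualifies for delay, or that Appendix 3 requires no discussion.* The footnote attaches to a figure that is not shown, so its grade and conditions cannot be seen. The *or* may mean that each limit applies to whichever test is raised, and silence in the footnote does not show that no consultation is required.
- *That there are three equal, competing rules for all high-grade rises.* The medical-monitor route is an exception within one rule, and its text reaches only Grade 3 AST or ALT.

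**Conclusion.** The inconsistency is real and should be corrected. Dose Delay Criteria omits an exception that Discontinuation Criteria contains. The marker and the text of that exception differ in scope. The Appendix 3 limits cover values for which Section 11.0 requires discontinuation, including the combined transaminase-bilirubin pattern. A patient could be permanently discontinued under one passage and held under another, with resumption possible only where Criteria to Resume Treatment allows it.

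The combined-pattern overlap rests on thresholds printed in the protocol, on the assumption that the unseen box does not exclude that pattern. The overlap for isolated Grade 3 rises also rests on cut-points that the documents do not give. If the pooled melanoma rates applied, at most about 5 patients (ALT) and 4 (AST) of 64 could be affected. These are overlapping ceilings from another schedule, not a forecast. The importance lies in the kind of decision involved more than in the number of patients.

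**What to change.** Reconcile Dose Delay Criteria, Criteria to Resume Treatment, Discontinuation Criteria and the Appendix 3 hepatic footnote into one consistent hepatic rule. The text should state:

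- whether any exception to discontinuation exists;
- which tests and grades it covers, with the asterisk and the footnote text agreeing;
- how the AST/ALT and bilirubin limits joined by *or* combine;
- how the exception relates to the combined AST/ALT-bilirubin criterion;
- who must be consulted;
- which text takes precedence where Section 11.0 and Appendix 3 differ.

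The choice of rule, limits and precedence is the sponsor's, and this point takes no position on it. The cost is a short amendment to Section 11.0 and a line in Appendix 3, with no effect on sample size or analysis.
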